6.8.5. Rescue Medicine for Atopic Dermatitis

To be consistent with real world practice, defined topical medications are allowed in this study (see Section 6.8.4). However, rescue therapies may be needed if the participant experiences intolerable clinical worsening of symptoms. Escalation to high potency topical TCS, topical JAK inhibitors, phototherapy and/or systemic medications (including but not limited to corticosteroids, immunosuppressants, biologics, small molecules, etc.) for the treatment of AD should only occur if participants do not respond adequately after at least 7 days of low/mid potency TCS, TCI and/or topical PDE4 inhibitors. Any use of topical JAKs, phototherapy, and/or systemic medications will be considered rescue therapy. Use of high-potency TCS for more than 10 days is also considered rescue therapy. Participants that receive Rescue therapy must be discontinued from the study. (see Section 7.1).

All rescue medication must be recorded in the CRF.

7. Discontinuation of Study Intervention and Participant Discontinuation/Withdrawal

Discontinuation of specific sites or of the study as a whole are handled as part of Appendix 1.

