#### 5.2.2. Supportive Estimands for the Primary Endpoint

There are two supportive estimands for the primary endpoint. The first is a hybrid estimand representing the following clinical question of interest: What is the intervention effect in percentage of participants achieving at least 75% improvement from baseline in Eczema Area and Severity Index (EASI) after 16 weeks of lebrikizumab 250 mg Q2W intervention in participants with moderate-to-severe AD who have been previously treated with dupilumab if all participants adhered to treatment except those who discontinued due to lack of efficacy?

This estimand is described by the following attributes:

- A. Population: participants with moderate-to-severe AD who have been previously treated with dupilumab.
- B. Endpoint: whether participants achieve at least 75% improvement from baseline in EASI at Week 16.
- C. Intercurrent events (ICEs): One ICE, permanent treatment discontinuation, is considered by this estimand as follows:
  - a. Participants who discontinue treatment due to lack of efficacy prior to Week 16 will be considered as treatment failures, i.e. non-responders, after the ICE. Therefore, a composite strategy is used for this type of ICE.
  - b. For participants who discontinue treatment due to reasons other than lack of efficacy prior to Week 16, a hypothetical strategy will be used to estimate what the treatment effect would have been if subjects continued with treatment. Therefore, a hypothetical strategy is used for this type of ICE.
- D. Population-level summary: percentage of participants achieving EASI-75 response at Week 16.

The second supportive estimand for the primary endpoint is a hypothetical estimand representing the following clinical question of interest: What is the intervention effect in percentage of participants achieving at least 75% improvement from baseline in Eczema Area and Severity Index (EASI) after 16 weeks of lebrikizumab 250 mg Q2W intervention in participants with moderate-to-severe AD who have been previously treated with dupilumab if all participants adhered to treatment?

This estimand is described by the following attributes:

A. Population: participants with moderate-to-severe AD who have been previously treated with dupilumab.

- B. Endpoint: whether participants achieve at least 75% improvement from baseline in EASI at Week 16.
- C. Intercurrent events (ICEs): One ICE, permanent treatment discontinuation, is considered by this estimand as follows:

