  - a. For participants who discontinue treatment prior to Week 16, a hypothetical strategy will be used to estimate what the treatment effect would have been if all subjects continued with treatment. Therefore, a hypothetical strategy is used for this type of ICE.
- D. Population-level summary: percentage of participants achieving EASI-75 response at Week 16.

## 5.2.3. Estimands for Secondary Endpoints at Week 16

The primary estimand for the primary endpoint will be applied to all secondary endpoints at Week 16. The supportive estimands for the primary endpoint will also be applied to all secondary endpoints at Week 16.

## 5.2.4. Estimands for Secondary Endpoints at Week 24

The primary estimand for the primary endpoint will be applied to all secondary endpoints at Week 24. There are two supportive estimands for secondary endpoints at Week 24. The first is a hybrid estimand representing the following clinical question of interest: What is the intervention effect in successful responses or means after 24 weeks of lebrikizumab intervention in participants with moderate-to-severe AD who have been previously treated with dupilumab if all participants adhered to treatment except those who discontinued due to lack of efficacy?

This estimand is described by the following attributes:

- A. Population: Treatment Period II population as described in Section 5.1.1.
- B. Endpoint: apply to all secondary endpoints at Week 24.
- C. Intercurrent events (ICEs): One ICE, permanent treatment discontinuation, is considered by this estimand as follows:
  - a. Participants who discontinue treatment due to lack of efficacy after Week 16 will be considered as treatment failures, i.e. non-responders, after the ICE. Therefore, a composite strategy is used for this type of ICE.
  - b. For participants who discontinue treatment due to reasons other than lack of efficacy after Week 16, a hypothetical strategy will be used to estimate what the treatment effect would have been if subjects continued with treatment. Therefore, a hypothetical strategy is used for this type of ICE.
- D. Population-level summary: percentage of successful responses or means at Week 24.

The second supportive estimand for secondary endpoints at Week 24 is a hypothetical estimand representing the following clinical question of interest: What is the intervention effect in successful responses or means after 24 weeks of lebrikizumab 250 mg Q2W intervention in

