participants with moderate-to-severe AD who have been previously treated with dupilumab if all participants adhered to treatment?

This estimand is described by the following attributes:

- A. Population: Treatment Period II population as described in Section 5.1.1.
- B. Endpoint: apply to all secondary endpoints at Week 24.
- C. Intercurrent events (ICEs): One ICE, permanent treatment discontinuation, is considered by this estimand as follows:
  - a. For participants who discontinue treatment after Week 16, a hypothetical strategy will be used to estimate what the treatment effect would have been if all subjects continued with treatment. Therefore, a hypothetical strategy is used for this type of ICE.
- D. Population-level summary: Population-level summary: percentage of successful responses or means at Week 24.

Because participants who initiate rescue medication are required to discontinue from the study and hence permanently discontinue study treatment, the supportive estimands for the primary and secondary endpoints only consider permanent treatment discontinuation as an ICE.

Analytical details on how missing data including those as a result of intercurrent events will be handled can be found in Section 5.4. The following table (Table KGBO.5.2) summarizes the analytical strategies that will be conducted on the intercurrent events for the five estimands.

		Analysis Stra Perman Disco	Missing Data		
Estimand	Population	Due to lack of efficacy	Due to any other reasons, including initiation of rescue medication	Imputation Method	
Primary Estimand for the Primary Endpoint and Secondary Endpoints	ITT Population who remained on treatment	Not applicable	Not applicable	Primary analysis: as observed	
Supportive Estimand for the Primary Endpoint and Secondary	ITT Population	Composite: Set to baseline	Hypothetical: Set to missing	MCMC-MI	

Endpoints at Week 16 (Hybrid)				
Supportive Estimand for the Primary Endpoint and Secondary Endpoints at Week 16 (Hypothetical)	ITT Population	Hypothetical: Set to missing	Hypothetical: Set to missing	LOCF
Supportive Estimand for Secondary Endpoints at Week 24 (Hybrid)	Treatment Period II Population	Composite: Set to baseline	Hypothetical: Set to missing	MCMC-MI
Supportive Estimand for Secondary Endpoints at Week 24 (Hypothetical)	Treatment Period II Population	Hypothetical: Set to missing	Hypothetical: Set to missing	LOCF

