# 5.4.3. Markov Chain Monte Carlo - Multiple Imputation (MCMC-MI)

The method of handling missing efficacy data relative to the supportive hybrid estimands for the primary and secondary endpoints at Week 16 will be based on Markov Chain Monte Carlo Multiple Imputation (MCMC-MI). For patients who discontinue treatment due to lack of efficacy prior to Week 16, set to the patient's baseline value subsequent to this time through Week 16. MCMC-MI will be used to handle the remaining missing data.

The method of handling missing efficacy data relative to the supportive hybrid estimand for secondary endpoints at Week 24 will be based on MCMC-MI. For patients who discontinue treatment due to lack of efficacy after Week 16, set to the patient's baseline value subsequent to this time through Week 24. MCMC-MI will be used to handle the remaining missing data. Imputation will be conducted within each treatment group independently so that the pattern of missing observations in one treatment group cannot influence missing value imputation in another.

For each imputation process, 25 datasets with imputations will be calculated. The initial seed values are given in Table KGBO.5.3. The response rates and their associated SEs will be computed for each data set using SAS PROC FREQ with the riskdiff option specified for the appropriate column in the TABLES statement. The response rates and SEs from the resulting output will be combined across the 25 imputed datasets using SAS PROC MIANALYZE.

For binary responses related to EASI and IGA, the binary response variables will be calculated based on the multiply imputed datasets that have been created. Because the MCMC algorithm is based on the multivariate normal model, imputed values for IGA will not generally be one of the discrete values used in IGA scoring (0, 1, 2, 3, or 4). Therefore, to derive the binary IGA response variable, standard rounding rules will be applied to the imputed values. For example, if a patient has an IGA score imputed as 1.4 (and assuming a baseline IGA score of 3), the imputed value would be rounded down to 1, and the minimum change from baseline of 2 would have been met. This patient would be considered a responder.

For derivation of an EASI-75 and EASI-90 response, no rounding will be performed. The imputed EASI value will be compared directly to the observed baseline EASI value to determine whether a reduction of at least 75% or 90% was achieved at each visit.

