## 5.7. Patient Disposition

The following patient disposition summaries will be provided (details of the analysis populations can be found in Section 5.1.1):

- The total number and percentage of patients entering each statistical analysis population as defined in Section 5.1.1 (analysis population: all entered patients).
- The number and percentage of patients who entered the study, were treated, and screen failed will be provided overall and by screen fail reason (analysis population: all entered patients).
- The number and percentage of patients who completed Week 16, and the number and percentage of patients who discontinued the treatment at any time before Week 16, by primary reason for discontinuation of treatment (analysis population: ITT).
- The number and percentage of patients who completed Week 24, and the number and percentage of patients who discontinued the treatment at any time before Week 24, by primary reason for discontinuation of treatment (analysis population: ITT).
- The number and percentage of patients who were treated and completed the study, and the number and percentage of patients who discontinued the study at any time, by primary reason for discontinuation (analysis population: ITT).

All enrolled participants (that is, in the ITT population) who discontinued from study treatment will be listed together with the discontinuation reason, and the timing of discontinuation from the study will be reported.

Patient allocation by center/site will be summarized with the number of patients who entered the study, number of ITT patients, number of patients discontinued from study treatment, and number of patients discontinued from the study.

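### The hybrid estimands count lack-of-efficacy exits as failures but impute exits for atopic dermatitis rescue as if treatment had continued

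*SAP*

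**What the plan says.** SAP Section 5.2.2 sets the hybrid question for Week 16 as the effect "if all participants adhered to treatment except those who discontinued due to lack of efficacy". Its failure rule is: "Participants who discontinue treatment due to lack of efficacy prior to Week 16 will be considered as treatment failures". Section 5.2.4 repeats this for Week 24: "Participants who discontinue treatment due to lack of efficacy after Week 16 will be considered as treatment failures". In both, discontinuation for any other reason takes a hypothetical strategy.

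Table KGBO.5.2 (Section 5.2.4) turns this into two columns. Lack of efficacy is set to baseline. The other column, headed "Due to any other reasons, including initiation of rescue medication", is set to missing and handled by MCMC-MI. Section 5.4.3 gives the operative imputation rule. It resets values to baseline only "For patients who discontinue treatment due to lack of efficacy prior to Week 16" (and correspondingly after Week 16), imputes everything else that is missing, and does not mention rescue.

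Protocol Section 6.8.5 says "rescue therapies may be needed if the participant experiences intolerable clinical worsening of symptoms" and that escalation "should only occur if participants do not respond adequately after at least 7 days of low/mid potency TCS, TCI and/or topical PDE4 inhibitors". Protocol Section 7.1 makes requiring rescue for AD symptoms a reason to discontinue study intervention permanently. Section 7.2 places study exit before the new agent is introduced.

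Neither document defines lack of efficacy. SAP Section 5.7 summarises those who "discontinued the treatment at any time before Week 16, by primary reason for discontinuation of treatment", so each exit carries one reason.

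**The concern.** By the Protocol's own description, someone who leaves because AD rescue is needed has worsened despite topical treatment. That is the group the composite part of the hybrid estimand exists to capture. The table instead imputes what that person's score would have been on continued treatment. The assignment is explicit, but for AD rescue it does not match the question in Sections 5.2.2 and 5.2.4.

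A second problem follows from the word initiation in the column head. If exit comes before the new agent, a participant can leave because rescue is required without having initiated it. That exit could be recorded as lack of efficacy and scored as failure, or recorded otherwise and imputed.

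The hybrid analysis is the only planned analysis with a failure rule. For responder endpoints, imputing these exits can only raise the rate relative to counting them as failures.

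**Working it through.** **1. The plan's own precision figure.** Inputs from SAP Section 4.2: N = 120, anticipated EASI-75 rate 50%, two-sided 90% Wilson interval, z = 1.645, z² = 2.706.

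Half-width = z × √[p(1−p)/n + z²/(4n²)] / (1 + z²/n) = 1.645 × √(0.002083 + 0.000047) / 1.0225 = 0.074.

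The interval is 42.6% to 57.4%, as in Table KGBO.4.1. The half-width of 7.4 points is the yardstick below.

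**2. How each exit is scored in the hybrid analysis.**

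| Exit | Rule that applies | Scoring |
|---|---|---|
| Recorded as lack of efficacy, no rescue | 5.2.2, 5.2.4, 5.4.3 | baseline value, non-responder |
| AD rescue initiated | Table KGBO.5.2 column head | missing, MCMC-MI |
| AD rescue required, not initiated | not stated; recorded reason decides | either |
| Rescue agent for a non-AD condition | Table KGBO.5.2 column head | missing, MCMC-MI |

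The last row fits the estimand: Protocol Section 6.8.2 counts any systemic corticosteroid use as rescue, and such use need not reflect AD failure. The second and third rows are the problem.

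**3. Formula.** Let r be the number who exit for AD rescue and q their mean imputed response probability. Excess in the responder rate = r × q / N. The documents give neither r nor q. I take r = 6 of 120 as an assumption, with 50% response in the other 114 (57 responders). If all six are failures, the rate is 57/120 = 47.5% (90% Wilson 40.1% to 55.0%).

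**4. Simulation for q.** Assumptions: N = 120 at both weeks; EASI at Weeks 0, 2, 4, 8, 16 and 24; about 50% EASI-75 at Week 16 and 55% at Week 24; normal-model imputation of raw EASI with 25 imputations; Week 24 imputed within Q2W and Q4W groups assigned by EASI-75 only; early-discontinuation (ED) EASI not used; adjacent-visit correlation 0.9 or 0.7; 1000 runs.

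| Six rescued participants are | q (corr. 0.9 / 0.7) | Excess, points |
|---|---|---|
| Week 16: the worst at Week 8 | 0.1% / 2.7% | 0.0 / 0.1 |
| Week 16: random | 41% / 40% | 2.1 / 2.0 |
| Week 24: worst inadequate responders | 0.7% / 8.4% | 0.0 / 0.4 |
| Week 24: random | 56% / 48% | 2.8 / 2.4 |
| Week 24: all Week 16 responders who relapse | 88% / 68% | 4.4 / 3.4 |

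If the six are imputed at the anticipated 50%, the Week 16 excess is 6 × 0.50 / 120 = 2.5 points. The excess scales with r: at q = 50%, r = 2 gives 0.8 point and r = 12 gives 5.0.

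**5. Why Week 24 can be worse.** Week 20 is a telephone visit, and the Schedule of Activities has no EASI between Weeks 16 and 24 except at ED. Without the ED score, a relapse after Week 16 is imputed from Week 16 or earlier. If the ED score records the worsening and is used, the excess is near 0. SAP Section 5.1 keeps out-of-window assessments in summaries, but the SAP does not say how an ED score enters the imputation.

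**The case against.** The strongest reply is that the table is itself the rule. Its columns are exclusive as worded, disposition uses one primary reason, and so every exit has a place. This stands in part. A reader might infer that the table contradicts the text, or that the plan has no rule for rescue. Neither holds: both send lack of efficacy to failure and other reasons to the hypothetical strategy, and the table does place initiated rescue. What remains is that this placement does not fit the hybrid question for AD rescue, and that it does not reach rescue that is required but not yet started.

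A reader might also infer that Appendix 1 of the SAP treats any systemic corticosteroid as AD rescue. Its definition and heading refer to systemic AD therapy; only the code list lacks an indication filter.

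On size, imputation uses earlier scores. If rescued participants were already doing badly, they are imputed as non-responders anyway and Week 16 barely moves. That is the profile closest to true AD failure, so the 2 to 2.5 point figure should not be taken as the expected one.

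Finally, all analyses are descriptive, the intervals are not a decision basis, and Protocol Section 7.2 expects few discontinuations. Exits are listed with reasons (SAP Section 5.7) and rescue use is summarised (Section 5.10), so a reader could partly reclassify them. These points limit the weight of the issue but do not remove the mismatch.

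**Conclusion.** The point holds for the supportive hybrid analyses at Weeks 16 and 24 only. A reader might infer that the primary result is biased; the documents do not support that. The as-observed primary analysis and the LOCF analyses do not use the split by reason.

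The true size is unknown. With the assumed 6 of 120 rescued, the Week 16 effect lies between negligible and roughly a third of the planned half-width (2.5/7.4 = 0.34). The largest Week 24 figures require all six to be Week 16 responders who relapse, with the ED EASI unused; the documents support neither condition. The simulated values also rest on the assumed response rates and correlations, and on 120 participants at Week 24, where the Treatment Period II population may be smaller.

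The case for changing the plan rests on the mismatch between estimand and handling, more than on the expected shift.

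**What to change.** Use one definition in Table KGBO.5.2 and SAP Sections 5.2.2, 5.2.4 and 5.4.3. For the hybrid estimands, lack of efficacy means discontinuation recorded with that reason, or discontinuation because rescue for AD was required or started, whatever primary reason is recorded. Apply the composite strategy to it: set to baseline, non-responder through Week 16 or Week 24. Remove rescue from the other-reasons column head, or limit it there to agents given for a non-AD condition, identified from the reason for use that Protocol Section 6.8 already requires to be recorded.

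Fix the rule before the primary lock. Because the study is open-label, limit medical review to confirming whether the indication was AD. Check that the discontinuation record can show that rescue was required; its categories are not in the documents.

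Protocol Sections 6.8.4 and 6.8.5 speak of participants who receive rescue, while Section 7.2 puts exit before the new agent. These passages should be reconciled so that required and started can be told apart.

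The cost is SAP wording and a short review of a few listed exits. The supportive hybrid rate may be slightly lower. No rescue or discontinuation rule changes, and the primary and LOCF analyses stay as planned.

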## 5.3. Adjustments for Covariates

No statistical tests will be performed.

## 5.4. Handling of Dropouts or Missing Data

Intercurrent events, as per the ICH guideline (ICH E9R1), are events which occur after the treatment initiation and make it impossible to measure a variable or influence how it should be interpreted. Examples of such events include treatment discontinuation due to death or AEs, rescue treatment, and loss to follow-up.

This section describes missing data imputation methods handling intercurrent events, which will be implemented in this study. For efficacy analyses relative to the primary estimand for primary and secondary endpoints, the method of handling missing data will be the "as observed" strategy described in Section 5.4.1.

For efficacy analyses relative to the supportive hypothetical estimands for primary and secondary endpoints, missing data including those because of intercurrent events will be imputed using the Last Observation Carried Forward (LOCF) strategy described in Section 5.4.2.

For efficacy analyses relative to the supportive hybrid estimands for primary and secondary endpoints, missing data including those because of intercurrent events will be imputed using Markov Chain Monte Carlo Multiple Imputation (MCMC-MI) as described in Section 5.4.3.

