#### 4.2. Determination of Sample Size

Based on available data, the anticipated EASI-75 response rate is approximately 50%. A total sample size of 120 enrolled participants will provide >95% probability that the half-width of the 2-sided 90% CI of the EASI-75 response rate is at most 10%.

Example point estimates for EASI-75 response rates and corresponding 2-sided 90% CIs based on the Wilson-Score method for a sample size of 120 participants are summarized in the table below. The CIs are provided as reference rather than a basis of any decision criteria.

Example Point Estimates	Lower Bound of 90% CI	Upper Bound of 90% CI
40%	32.9%	47.5%
45%	37.7%	52.5%
50%	42.6%	57.4%
55%	47.5%	62.3%
60%	52.5%	67.1%

Table KGBO.4.1 Estimated 90% CI with Sample Size of 120 Participants

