### 5.4.2. Last Observation Carried Forward

In this analysis, all missing values will be imputed using last observation carried forward (LOCF). Baseline values will be used for imputation if there is no postbaseline observation.

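### The supportive all-adhered estimands are estimated only by LOCF, on an unstated assumption and by a different method from the hybrid estimands

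*SAP*

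**What the plan says.** **Target.** For the second supportive estimand of the primary endpoint, SAP 5.2.2 says that "a hypothetical strategy will be used to estimate what the treatment effect would have been if all subjects continued with treatment". SAP 5.2.4 sets the same target for all secondary endpoints at Week 24, in the Treatment Period II population.

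**Estimator.** For these hypothetical estimands SAP 5.4 says that "missing data including those because of intercurrent events will be imputed using the Last Observation Carried Forward (LOCF) strategy". SAP 5.4.2 has two sentences: every missing value takes the last observation, and "Baseline values will be used for imputation if there is no postbaseline observation". It gives no assumption and no reason.

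**Hybrid estimands.** Table KGBO.5.2 sets lack-of-efficacy stops to baseline. The column headed "Due to any other reasons, including initiation of rescue medication" holds the entry "Hypothetical: Set to missing" in both the hybrid and the hypothetical rows. The imputation method beside it is MCMC-MI for the hybrid and LOCF for the hypothetical. SAP 5.4.3 confirms that, after the baseline substitution, "MCMC-MI will be used to handle the remaining missing data".

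**Reporting.** SAP 5.11 and 5.12 report as-observed, LOCF and MCMC-MI summaries.

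**Schedule (Protocol 1.3).** EASI and IGA are scheduled at screening, Weeks 0, 2, 4, 8, 16 and 24, and at early discontinuation (ED). Weeks 12 and 20 are telephone contacts. DLQI, cDLQI and SCORAD are scheduled only at Weeks 0, 16, 24 and ED. Itch, sleep loss and skin pain are daily diary items.

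**The concern.** LOCF describes where a participant was when last seen. The estimand asks where participants would have been had they stayed on treatment. For a response rate the two agree only if stoppers' rate under continued treatment equals the rate among their carried values. For a continuous endpoint the two means must agree. The SAP makes this equality the sole basis of the all-adhered figure without saying so.

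The assumption is most demanding for EASI and IGA when no ED value is available. The Week 16 result is then a value from Week 8 or earlier, and the Week 24 result is the Week 16 value. The daily diary measures do not share this gap.

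The second problem is comparability. The hybrid and hypothetical estimands differ, by definition, only in how they treat lack-of-efficacy stops. Because the other stops are also imputed differently, the gap between the two results mixes a change of question with a change of method.

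**Working it through.** **Plan's own figure.** SAP 4.2 states that "the anticipated EASI-75 response rate is approximately 50" percent, for all participants, with N = 120 and a two-sided 90% Wilson interval. With z = 1.645, the half-width at 60/120 is z × √(0.25/120 + z²/(4 × 120²)) / (1 + z²/120) = 7.4 points. The interval is 42.6% to 57.4%, as printed. It does not depend on the imputation method and serves here as a yardstick.

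**Inputs the documents do not give.** Protocol 7.2 expects discontinuation to be uncommon but states no rate. The following are therefore assumptions:
- d = share stopping before Week 16
- r = stoppers' EASI-75 rate had they continued
- q = EASI-75 rate among their carried values

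**Step 1: error of LOCF against its own target.** Those who stay contribute equally to both, so shortfall = d × (r − q). Example: 0.10 × (0.50 − 0.25) = 2.5 points, or 3.0 of 120 participants. With q = 25% (negative means LOCF is too high):

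| d | r = 20% | r = 30% | r = 40% | r = 50% |
|---|---|---|---|---|
| 5% | −0.25 | 0.25 | 0.75 | 1.25 |
| 10% | −0.5 | 0.5 | 1.5 | 2.5 |
| 20% | −1.0 | 1.0 | 3.0 | 5.0 |

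r = 50% is the upper end shown because it gives stoppers the rate anticipated for everyone. The choice of q matters. At r = 50% and q = 0%, 10%, 20%, 30%, the shortfall is 2.5, 2.0, 1.5, 1.0 points at d = 5%, and 5.0, 4.0, 3.0, 2.0 at d = 10%.

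**Step 2: LOCF hypothetical against hybrid.** Split the stops into lack of efficacy (dL) and other (dO), let p be the rate among those who stay, and take MCMC-MI to return rO for the other stops.
- Hybrid = (1 − dL − dO) × p + dL × 0 + dO × rO
- LOCF = (1 − dL − dO) × p + dL × qL + dO × qO
- LOCF − hybrid = dL × qL − dO × (rO − qO), so p cancels

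For illustration, take p = 50%, dL = 2%, dO = 8%, qO = 25%. Those who stay contribute 0.90 × 50% = 45.0%.

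| rO | Hybrid | LOCF − hybrid, qL = 0 (LOCF 47.0%) | LOCF − hybrid, qL = 20% (LOCF 47.4%) |
|---|---|---|---|
| 20% | 46.6% | +0.4 | +0.8 |
| 30% | 47.4% | −0.4 | 0.0 |
| 40% | 48.2% | −1.2 | −0.8 |
| 50% | 49.0% | −2.0 | −1.6 |

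The all-adhered rate falls below the hybrid when rO > qO + dL × qL / dO. That threshold is 25% at qL = 0 and 25% + 0.02 × 20% / 0.08 = 30% at qL = 20%.

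**Step 3: like handling.** If MCMC-MI is used for both, hypothetical − hybrid = dL × rL, where rL is the rate lack-of-efficacy stoppers would have had if they had continued. This cannot be negative apart from imputation noise. For rL = 0 to 30% it is 0 to 0.02 × 30% = 0.6 point.

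**Week 24.** The same formulas apply in the Treatment Period II population, with d the share stopping after Week 16. The documents offer no further inputs, so no separate figures are given.

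**The case against.** The strongest reply has four parts.

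1. **MCMC-MI results are already planned for every primary and secondary endpoint, and disposition is reported by reason.** This is true, but it does not fill the gap. The dataset in SAP 5.4.3 sets lack-of-efficacy stops to baseline, so it estimates the hybrid. The reply is right that a properly aligned run would move little from that result: 0 to 0.6 point in the illustration.

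2. **The method is disclosed.** This also stands. Table KGBO.5.2 names LOCF, and SAP 5.4.2 gives the carry and the baseline fallback. What is missing is the assumption that links LOCF to the estimand.

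3. **Stoppers are sent to an ED visit.** Protocol 7.1 and 7.2 require one where applicable, and EASI and IGA are scheduled there. For rescue, Protocol 7.2 places discontinuation before the new agent, so an ED value may capture the worsening that led to the stop. The long carry therefore arises only when no ED value is available.

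4. **MCMC-MI has unstated assumptions too.** SAP 5.4.3 states only the normal model ("Because the MCMC algorithm is based on the multivariate normal model") and does not mention missing at random. This is correct, and the fix has to include that statement. A sentence in SAP 5.4.2 defending LOCF would be a smaller repair. It would end the silence but leave the two supportive results non-comparable.

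**Conclusion.** The point holds as a low-priority improvement. The all-adhered estimands rest on LOCF alone with no stated assumption, and stops with the same table entry are imputed by two methods without a reason.

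The size is small if discontinuation is uncommon. With q = 25% and r = 20% to 50%, LOCF runs from 0.25 point too high to 1.25 too low at 5% stopping, and from 0.5 too high to 2.5 too low at 10%. The yardstick is 7.4 points. These values of d, r and q, and the 2%/8% split, are assumptions. Other values of q shift the range.

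A reader might infer more than the documents support:
- **That LOCF is conservative here.** The direction is not fixed. LOCF is too low if stoppers would have improved further and too high if they would have worsened. The other-reason stops include rescue starters, and Protocol 6.8.5 ties rescue to worsening.
- **That each participant's last value must persist.** For a rate, equality on average (r = q) is enough.
- **That the all-adhered rate will fall below the hybrid.** It can, but in the illustration only when rO exceeds 25% to 30%.
- **That the main result is affected.** The primary analysis is as observed, and nothing is tested. Only supportive, descriptive summaries are involved.

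**What to change.** 1. In Table KGBO.5.2 and SAP 5.4, estimate the hypothetical estimands at Weeks 16 and 24 by the MCMC-MI procedure of SAP 5.4.3, with all post-discontinuation values set to missing and none set to baseline. Add seed values for this run to Table KGBO.5.3.
2. State the missing-at-random assumption alongside the multivariate normal model.
3. Keep LOCF as a labelled descriptive summary not tied to an estimand.
4. State whether an ED-visit value counts as an observation, and apply one rule in both supportive analyses. SAP 5.4.2 naturally covers an ED value as a postbaseline observation, but the set-to-missing entry leaves doubt. The rule matters most for DLQI, CDLQI and SCORAD, whose only scheduled postbaseline value before Week 16 is at ED.

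**Cost.** SAP wording and one more run of a program already planned, with no new data. MI brings its own missing-at-random and normality assumptions. It will lie close to the as-observed result for DLQI, CDLQI and SCORAD, which have little intermediate data. It will be imprecise for CDLQI, which covers only those under 16, a subset of about 12 planned adolescents.
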